5.4. Immunogenicity Per Protocol Set

The immunogenicity PP (IPP) set will consist of the subset of subjects who participated in the immunogenicity portion of the study, who had a Day 21 immunogenicity sample collection; who had no major deviations related to subject eligibility, the ability to develop a valid immune response, prohibited medication use, or the immunogenicity analyses; and who received the vaccine or the active comparator. Subjects who received the wrong treatment, but for whom the treatment received can be unequivocally confirmed, will be analyzed as treated, provided they have no other deviations that compromise their data.

The analyses of all immunogenicity endpoints will be performed using the IPP set.

5.5. Protocol Deviations

A protocol deviation is any change, divergence, or departure from the study design or procedures of a study protocol. Major and minor protocol deviations will be identified and documented during a blinded data review prior to database lock. Subjects will be excluded from analyses if the deviation is considered to impact the analyses.

Prematurely terminating study participation for reasons such as withdrawal of consent or occurrence of adverse events (including death) is not considered as a protocol deviation. The missing assessments that should have otherwise been collected for that subject later in the study are also not considered as a protocol deviation.

Protocol deviations will be reviewed by Medicago (or its designee) to identify any non-compliances likely to have a significant effect on the safety and rights of a subject or the reliability and robustness of the data generated. These deviations will be included in the clinical study report.

6. GENERAL ASPECTS FOR STATISTICAL ANALYSIS

6.1. General Methods

All statistical procedures will be completed using (SAS®) version 9.4 or higher.

Unless otherwise stated, all statistical testing will be two-sided and will be performed using a significance (alpha) level of 0.05. Two-sided 95% confidence intervals (CI) will be provided when relevant.

Continuous variables will be summarized using descriptive statistics, including number of subjects (n), mean, median, standard deviation (SD), minimum (Min) and maximum (Max).

For categorical variables, summaries will include counts of subjects and percentages. Percentages will be rounded to one decimal place.

All summaries will be presented by treatment group and age group, unless otherwise specified.

All subject data, including those derived, will be presented in individual subject data listings. All listings will be sorted by subject number, date/time and visit. The vaccine group (VLP and Comparator) as well as subject's age stratum will be stated on each listing.

A subject who is randomized but does not receive study drug will be included in the subject data listings. All pre- and post-vaccination results, including repeated and unscheduled assessments, will be included in the data listings. Data collected at unscheduled visits that occurred outside the time windows specified in the protocol will be included in the data listings but will not be included in the analyses.

6.2. Reporting Precision

The following decimal description will be used for the demography, efficacy, immunogenicity and safety analyses.

Category	Parameters	Number of Decimal Digits
Demographic characteristics	Mean, Median	1 (One more decimal place than the raw data)
	SD	2 (Two more decimal place than the raw data)
	Min, Max	0 (Same number of decimal places as the raw data)
	% of count	1
Efficacy	VE & 95% CI	1
Humoral and Cellular Immunogenicity evaluation	GMTs including LL & UL of 95% CI	1
	GMFR including LL & UL of 95% CI	2
	SC & SP rate including LL & UL of 95% CI	1
	CMI mean, median	1

Category	Parameters	Number of Decimal Digits	
	CMI SD	2	
	P-Value	3 (0.xxx format)	
Safety	% of count	1	

For some parameters (% of count, 95% CI and VE), careful consideration may be required in some instances (e.g. very low-incidence) and in such situations, details will be described in footnotes or programming notes.

6.3. Key Definitions and Derivations

6.3.1. Baseline Values

Unless otherwise specified, the last observed measurement prior to the dose of trial vaccine will be considered as the baseline measurement.

6.3.2. Study Day

Study Day is the number of days since the administration of the study vaccine, which is counted as Study Day 0. If the assessment date is after the date of the vaccination, the study day is calculated as date of assessment - date of the vaccination + 1. If the assessment date is prior to the date of the vaccination, the study day is calculated as date of assessment - date of the vaccination.

6.3.3. Onset day

Onset day is calculated as date of event – date of the vaccination +1.

6.3.4. Demographics

Age collected in CRF will be used on tables.

BMI (kg/m^2) is calculated using the following formula:

BMI=Weight (kg) / Height² (m²)

6.3.5. Immunogenicity

Values below the HI antibody responses below the lower limit of quantification (Below limit of Quantification (BLQ)<10, recorded as "< 10") will be attributed a value of 5. All BLQ responses for the SRH antibody will be attributed a value of 2 mm².

For HI assay:

SC rate is defined as the proportion of subjects in a given treatment group with either $a \ge 4$ -fold increase in reciprocal HI titers between Day 0 and Day 21 or a rise of undetectable HI titer (i.e. < 10) pre-vaccination (Day 0) to an HI titer of ≥ 40 on Day 21.

SP rate is defined as the proportion of subjects in a given treatment group attaining a reciprocal HI titer of ≥ 40 on Day 21 (the percentage of vaccine recipients with a serum HI titer of at least 1:40 following vaccination).

For MN assay:

SC rate is defined as the proportion of subjects in a given treatment group with either $a \ge 4$ -fold increase in reciprocal MN titers between Day 0 and Day 21 or a rise of undetectable MN titer (i.e. 7.1) pre-vaccination (Day 0) to an MN titer of ≥ 28.3 at Day 21 post-vaccination.

For SRH assay:

SC rate is defined as the proportion of subjects in a given treatment group showing at least 50 % increase in GMA between Days 0 and 21.

SP rate is defined as the proportion of subjects in a given treatment group attaining an area $\geq 25 \text{ mm}^2$ following vaccination (Day 21).

GMT calculation:

The GMT calculations are performed by taking the anti-log of the mean of the log titer transformations. The back-transformation for mean GMT will be calculated with two-sided, 95% confidence limits, based on the Analysis of Variance (ANOVA) model.

GMFR calculation:

The GMFR will be derived by using Analysis of Covariance (ANCOVA) to model the difference in the log of the titer values between Day 21 and Day 0, with treatment group as main effect and baseline titer as covariate. The GMFR will be compared between the treatment groups. The comparisons between the treatment groups will be performed using two-sided, 95% confidence, based on the least-squares mean differences from the ANCOVA model.

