10.4.2.1 Secondary Endpoints

- HI antibody response induced against the homologous and heterologous influenza strains on Days 0 and 21 in a subset of 420 subjects (210 from each of the two treatment groups). HI antibody titers will be analyzed as follows:
 - GMT of HI antibody on Days 0 and 21;
 - SC rate: the proportion of subjects in a given treatment group with either a ≥ 4-fold increase in reciprocal HI titers between Day 0 and Day 21 or a rise of undetectable HI titer (i.e. < 10) pre-vaccination (Day 0) to an HI titer of ≥ 40 on Day 21;
 - SP rate: the proportion of subjects in a given treatment group attaining a reciprocal HI titer of ≥ 40 on Day 21 (the percentage of vaccine recipients with a serum HI titer of at least 1:40 following vaccination);
 - Geometric mean fold rise (GMFR): the geometric mean of the ratio of GMTs (Day 21/Day 0).
- MN antibody response induced by the Quadrivalent VLP Influenza Vaccine against the homologous influenza strains on Days 0 and 21, in the subset of subjects, will be analysed as follows:
 - GMT of MN antibody on Days 0 and 21;
 - SC rate on Day 21 (as defined above for HI);
 - GMFR (Day 21/Day 0).
- SRH antibody response induced by the Quadrivalent VLP Influenza Vaccine against the homologous strains on Days 0 and 21 in a subset of subjects, will be analysed as follows:

Medicago R&D Inc. Page 57 of 90

- Geometric mean area (GMA) of SRH antibody on Days 0 and 21;
- SC rate: proportion of subjects in a given treatment group showing at least 50 % increase in GMA between Days 0 and 21;
- SP rate: the proportion of subjects in a given treatment group attaining an area diameter ≥ 25 mm² following vaccination (Day 21);
- GMFR: the geometric mean of the ratio of GMA (Day 21/Day 0).

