4.3. Immunogenicity Endpoints

4.3.1. Secondary Endpoints

HI antibody response induced against the homologous and heterologous influenza strains on Days 0 and 21 in a subset of 420 subjects (210 from each of the two treatment groups). HI antibody titers will be analyzed as follows:

- 1. Geometric mean titer (GMT) of HI antibody on Days 0 and 21;
- 2. Seroconversion (SC) rate: the proportion of subjects in a given treatment group with either a ≥ 4-fold increase in reciprocal HI titers between Day 0 and Day 21 or a rise of undetectable HI titer (i.e. < 10) pre-vaccination (Day 0) to an HI titer of ≥ 40 on Day 21;
- 3. Seroprotection (SP) rate: the proportion of subjects in a given treatment group attaining a reciprocal HI titer of \geq 40 on Day 21 (the percentage of vaccine recipients with a serum HI titer of at least 1:40 following vaccination);
- 4. Geometric mean fold rise (GMFR): the geometric mean of the ratio of GMTs (Day 21/Day 0).

MN antibody response induced by the Quadrivalent VLP Influenza Vaccine against the homologous influenza strains on Days 0 and 21, in the subset of subjects, will be analyzed as follows:

- 1. GMT of MN antibody on Days 0 and 21;
- 2. SC rate on Day 21: the proportion of subjects in a given treatment group with either $a \ge 4$ -fold increase in reciprocal MN titers between Day 0 and Day 21 or a rise of

undetectable MN titer (i.e. 7.1) pre-vaccination (Day 0) to an MN titer of \geq 28.3 at Day 21 post-vaccination

3. GMFR: the geometric mean of the ratio of GMT (Day 21/Day 0).

SRH antibody response induced by the Quadrivalent VLP Influenza Vaccine against the homologous strains on Days 0 and 21 in a subset of subjects, will be analyzed as follows:

- 1. Geometric mean area (GMA) of SRH antibody on Days 0 and 21;
- 2. SC rate: proportion of subjects in a given treatment group showing at least 50 % increase in GMA between Days 0 and 21;
- 3. SP rate: the proportion of subjects in a given treatment group attaining an area ≥ 25 mm² following vaccination (Day 21);
- 4. GMFR: the geometric mean of the ratio of GMA (Day 21/Day 0).

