9.2. Analysis of Secondary Endpoints

The secondary immunogenicity endpoints are defined in Section 4.3.1.

HI antibody titers will be analyzed and evaluated as follows:

- GMTs of HI antibody: The point estimates and the corresponding two sided 95 % CI by treatment group and strain will be calculated as the antilog of the mean and 95 % CI of log transformed titer values on Days 0 and 21;
- SC rate: The point estimates and the corresponding two-sided 95 % CI for subjects achieving SC by treatment group and strain will be calculated and reported;
- SP rate: The point estimates and the corresponding two-sided 95 % CI for subjects achieving SP by treatment group and strain will be calculated and reported.
- GMFR: the geometric mean of the ratio of GMTs (Day 21/Day 0).

MN antibody response against the homologous influenza strains on Days 0 and 21 will be analyzed as follows:

- GMTs of MN antibody on Days 0 and 21(as defined above for HI);
- SC rate: the proportion of subjects in a given treatment group with either a ≥ 4-fold increase in reciprocal MN titers between Day 0 and Day 21 or a rise of undetectable MN titer (i.e. 7.1) pre-vaccination (Day 0) to an MN titer of ≥ 28.3 at Day 21 post-vaccination.
- GMFR: the geometric mean of the ratio of GMTs (Day 21/Day 0).

SRH antibody response against the homologous influenza strains will be analyzed as follows:

- GMAs of SRH antibody on Days 0 and 21;
- SC rate: proportion of subjects in a given treatment group showing at least 50% increase in GMA between Days 0 and 21;
- SP rate: the proportion of subjects in a given treatment group attaining an area ≥ 25 mm² following vaccination (Day 21);
- GMFR: the geometric mean of the ratio of GMAs (Day 21/Day 0).

The GMFR will be derived by using ANCOVA to model the difference in the log of the titer values between Day 21 and Day 0, with treatment group as main effect and baseline titer as covariate

The GMTs, GMFRs, SP and SC rates of the HI antibody assay, the GMTs, GMFRs and SC rates of and the MN antibody assay, and the GMAs, GMFRs, SC rates, and SP rates for the SRH antibody assay will be compared between the treatment groups using descriptive statistics and 95% CI.

For SC rate and SP rate, Fisher's exact tests will be used. GMT for HI, MN and GMA for SRH will be compared between treatment groups using the ANOVA model. GMFR for HI, MN and SRH will be compared using the ANCOVA model.

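### SRH seroconversion has no rule for a below-limit baseline: with such results set to 2 mm², a subject counts as seroconverted at 3 mm², or at the first quantifiable Day 21 reading

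*SAP*

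**What the plan says.** The SRH seroconversion rule appears in four places with the same content: Protocol 10.4.2.1 and SAP 4.3.1, 6.3.5 and 9.2. SAP 4.3.1 has "SC rate: proportion of subjects in a given treatment group showing at least 50 % increase in GMA between Days 0 and 21". None of the four gives a minimum Day 21 area or says what to do when the Day 0 result is below the limit.

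SAP 6.3.5 fixes the value such results take: "All BLQ responses for the SRH antibody will be attributed a value of 2 mm²". It gives the HI limit (10, with values below it set to 5) but no SRH limit. SRH seroprotection is a Day 21 area of at least 25 mm².

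The other two assays each have a clause for an undetectable baseline, as an alternative to a rise of at least 4-fold. For HI it is "undetectable HI titer (i.e. < 10) pre-vaccination (Day 0) to an HI titer of ≥ 40 on Day 21"; for MN it is "undetectable MN titer (i.e. 7.1) pre-vaccination (Day 0) to an MN titer of ≥ 28.3 at Day 21 post-vaccination".

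Under SAP 9.2, seroconversion rates are compared between arms by Fisher's exact test. SAP section 12 records a change to the MN seroconversion definition and none for SRH.

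**The concern.** A ratio criterion needs a measured denominator. For a subject with a BLQ baseline the denominator is a constant chosen in the SAP, so the 50% rise is not a rise over anything observed in that subject. If the constant is low relative to the assay limit, the criterion excludes no quantifiable result: a small zone just above the limit and a zone of 25 mm² are the same response.

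The wording adds a second problem. Seroconversion is a per-subject status, but the rule asks for an increase in GMA, a geometric mean over a group. The individual zone area must be meant, and a programmer should not have to infer that.

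At stake is the meaning of one secondary endpoint. A reader of the report would see an SRH seroconversion rate and could not tell how much of it comes from subjects who became merely quantifiable. The protocol (1.3.2.1 and 1.4) describes weaker humoral responses in the elderly, so low-level rises are plausible in this population.

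**Working it through.** **Inputs.** BLQ value for SRH: 2 mm² (SAP 6.3.5). Required rise: 50%, a ratio of 1.5 (Protocol 10.4.2.1; SAP 4.3.1, 6.3.5, 9.2). SRH seroprotection area: 25 mm² (SAP 4.3.1, 6.3.5). SRH limit of quantification, L: not given; assumed range 2 to 10 mm². The plan states no SRH threshold or expected rate, so there is no figure of its own to reproduce.

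**Step 1: threshold implied by the rule.** Day 21 threshold = 1.5 × Day 0 value = 1.5 × 2 = 3 mm². As a share of the seroprotection area, 3 / 25 = 12%. Reaching 25 mm² from 2 mm² would be 25 / 2 = 12.5-fold. A subject who is BLQ on both days has a ratio of 2 / 2 = 1 and is not a responder.

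**Step 2: effect of the unstated limit.** The smallest quantifiable Day 21 area that seroconverts is the larger of L and 3.

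| Assumed L (mm²) | Smallest seroconverting area (mm²) | Ratio to 2 mm² | Share of 25 mm² |
|---|---|---|---|
| 2 | 3 | 1.5 | 12% |
| 3 | 3 | 1.5 | 12% |
| 4 | 4 | 2.0 | 16% |
| 5 | 5 | 2.5 | 20% |
| 8 | 8 | 4.0 | 32% |
| 10 | 10 | 5.0 | 40% |

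For every L of 3 mm² or more, all quantifiable Day 21 results after a BLQ baseline are seroconversions. If 2 mm² is half the limit, as 5 is half of 10 for HI, then L = 4 mm². In that case 3 mm² is itself below the limit, and the test is whether a quantifiable zone appears.

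**Step 3: comparison with HI and MN.** HI seroconversion is met by either of two limbs. With BLQ set to 5, the 4-fold limb is met at 4 × 5 = 20, which is 20 / 40 = 50% of the seroprotection titer and twice the limit of 10. For MN, 4 × 7.1 = 28.4 against the stated 28.3, so the undetectable limb adds practically nothing to the 4-fold rule. SRH therefore differs from HI in degree (12% of the seroprotection level against 50%), and from both assays in saying nothing about an undetectable baseline.

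**Step 4: the replacement rule.** Require 25 mm² on Day 21 after a BLQ baseline, and leave the 50% rule for quantifiable baselines. Anyone from a BLQ baseline who reaches 25 mm² also passes 3 mm², and the other limb is unchanged. The new responders are thus a subset of the present ones, and the rate in each arm stays the same or falls.

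**The case against.** The strongest reply has four parts.

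*HI and MN impose no firm floor either.* This stands. A reader might infer that SRH lacks a Day 21 minimum that the other assays enforce. The either/or wording does not support that: HI accepts 5 to 20, and MN's 28.3 is essentially 4 × 7.1.

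*The constant often does not decide the outcome.* This stands in part. With L = 4, any assigned value up to 4 / 1.5 = 2.67 mm² gives the same responders. It would be wrong to say that the choice of 2 rather than the vaccine determines response. But this is the point in another form: in that range the 50% criterion does no work. Nor can such responses be dismissed as assay noise. That would need the limit and the assay's precision, and a change from undetectable to quantifiable may be real.

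*The 25 mm² requirement creates a discontinuity.* This stands as a cost. With L = 4, a subject going from 4 to 6 mm² seroconverts (6 / 4 = 1.5), while one going from BLQ to 24 mm² (24 / 2 = 12-fold on the assigned value) does not. For BLQ-baseline subjects, seroconversion also coincides with seroprotection.

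*The consequences are small.* Largely right. The endpoint covers 420 of about 12,120 subjects and has no success criterion; the 30% and 60% bounds in Protocol 12.6.1 apply to HI. The same rule applies in both arms, and no comparison of rates across assays is planned. SRH seroprotection, GMA, GMFR, reverse cumulative distribution curves and listings are also planned and would show low-level responses.

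**Conclusion.** The point holds as a flaw in a stated rule, with limited reach. After a BLQ baseline, SRH seroconversion is reached at 3 mm² by arithmetic on the plan's own numbers. It is reached at any quantifiable area if the limit is 3 mm² or more. Across assumed limits of 2 to 10 mm² the first qualifying reading is 3 to 10 mm², always below 25 mm².

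Two further inferences are not supported. A reader might conclude that the rule inflates both arms equally and so pulls them together. An equal addition to both rates leaves their difference unchanged, and an unequal one could widen or narrow it; the documents do not show which would occur. A reader might also want a size for the overstatement. It would be the proportion with a BLQ baseline times the proportion of those with a Day 21 area that qualifies now but is below 25 mm². For example, 0.30 × 1/3 = 0.10, or 10 percentage points, but both inputs are pure assumption and the documents have no SRH baseline data. The product may be anywhere from zero up to the BLQ proportion itself.

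What is established is a loss of interpretability in one secondary immunogenicity endpoint. The efficacy analyses are untouched.

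**What to change.** In SAP 4.3.1, 6.3.5 and 9.2:

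- State the SRH limit of quantification.
- Replace GMA in the seroconversion rule with the subject's own zone area.
- Define SRH seroconversion as (a) Day 0 BLQ and a Day 21 area of at least 25 mm², or (b) Day 0 quantifiable and at least a 50% increase in area. Limb (a) uses the SAP's seroprotection level, as the undetectable limb for HI uses 40.
- Use the 2 mm² value for GMA and GMFR only.
- Report the present 50% rule, with BLQ baselines at 2 mm², as a sensitivity analysis.
- List the change in SAP section 12. It departs from Protocol 10.4.2.1, and the MN definition there is a precedent for the SAP prevailing.

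The cost is a few lines of text, one changed derivation and one extra table; no new data are needed. The price is a rate in each arm that is the same or lower, and a stricter demand on BLQ-baseline subjects than on those with a low quantifiable baseline. The sensitivity analysis lets a reader see how much that matters.

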9.2.2. Methodology for computing CI

9.2.2.1. 95% CIs

The 95% CI for GMTs will be obtained within each group separately. The 95% CI for the mean of log-transformed titer/concentration will be first obtained assuming that log-transformed concentrations/titers are normally distributed with an unknown variance. The 95% CI for GMTs will be then obtained by exponential-transformation (anti-log with power 10) of the 95% CI for the mean of log-transformed titers.

SAS® Code for comparing GMTs:

```
PROC MIXED DATA=<Data>; * specify and sub-select data set as applicable;
    *BY Agegrp; * as applicable;
CLASS trtpn; * other factors may be added, if applicable;
MODEL AVAL = trtpn; * AVAL=logtiter
```

```
* add factors and options (e.g. ALPHA=.. Solutions) as applicable;
  LSMEANS trtpn / CL ALPHA=0.05 STDERR; * modify/adapt as applicable
  Ods output LSMEANS = outmix;
RUN;
QUIT;
Data _outmix;
Set outmix;
   GMT= 10**(Estimate);
   GMT LCL = 10**(Lower);
   GMT UCL = 10**(Upper);
RUN:
SAS® Code for comparing GMFR:
PROC MIXED DATA=<Data> (analysis dataset);
      class trtpn;
      model diff= trtpn Base; * diff = log10Day21 - log10Day0. Base=log10Day0
      Lsmeans trtpn/cl alpha=0.05;
      Ods output LSMEANS = outmix;
run;
Quit;
Data outmix;
Set outmix;
   GMFR = 10**(Estimate);
   GMFR LCL = 10**(Lower);
   GMFR_UCL = 10**(Upper);
Run;
```

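### Each arm's GMFR is defined as an unadjusted Day 21/Day 0 fold rise, but the SAP derives and prints it as a baseline-adjusted ANCOVA least-squares mean

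*SAP*

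**What the plan says.** SAP 4.3.1 gives the HI endpoint as "Geometric mean fold rise (GMFR): the geometric mean of the ratio of GMTs (Day 21/Day 0"), and SAP 9.2 repeats it: "GMFR: the geometric mean of the ratio of GMTs (Day 21/Day 0"). Protocol 10.4.2.1 has the same wording, "the geometric mean of the ratio of GMTs (Day 21/Day 0"). None of these mentions a covariate. The MN and SRH endpoints follow the same pattern, SRH with areas in place of titers.

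The derivation is different. SAP 6.3.5 says "The GMFR will be derived by using Analysis of Covariance (ANCOVA) to model the difference in the log of the titer values" between the two days, "with treatment group as main effect and baseline titer as covariate", and SAP 9.2 says so again after restating the plain definition. The sample code in SAP 9.2.2.1 fits "model diff= trtpn Base; * diff = log10Day21 - log10Day0. Base=log10Day0", takes the least-squares (LS) mean of each arm with 95% limits, raises 10 to those values, and names the results GMFR and its lower and upper limits.

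Two further places matter. Protocol 12.6.1 foresees analysis of variance models for GMFR only to compare the groups (MN and SRH). SAP section 12 declares four changes from the protocol, one of them as fine as the MN seroconversion cut-off, but not this derivation.

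**The concern.** One secondary endpoint has two specifications, and a programmer who follows the code will not print the defined one. The GMTs come from a model with treatment only, so their LS means are plain arm means. For subjects with both samples, GMT Day 21 divided by GMT Day 0 should therefore equal the GMFR exactly, but with the ANCOVA output it generally will not. SAP 6.2 reports GMFR to two decimals, so the gap can be visible.

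The interval is affected too. The LS-mean standard error uses the residual SD after baseline is removed, pools it over the arms, and treats the observed overall baseline mean as a fixed number. That suits a prediction at that baseline, but it is not in general the right error for an arm's mean fold rise in the population.

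The code also leaves out the quantity for which ANCOVA is well suited. SAP 6.3.5 bases the group comparison on LS-mean differences, but the GMFR code requests LS means by arm and no difference. The mismatch touches three assays, every strain tested and both arms, overall and by age group.

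**Working it through.** The plan states no GMFR, SD, correlation or CI width for the immunogenicity subset, so there is no figure of its own to reproduce.

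**Inputs from the documents.** n = 210 per arm (SAP 4.3.1). With the 2:1 age split this is about 140 and 70 per arm by age stratum. Intervals are two-sided 95%.

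**Assumed inputs.** Day 0/Day 21 correlation of log10 titers ρ from 0.2 to 0.9; SD of log10 titer s = 0.5 on both days and in both arms unless stated.

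**Point estimate.** LS mean for an arm = mean(diff) − b × (arm baseline mean − overall baseline mean). It equals the defined quantity only if b = 0 or the arm baselines coincide. With equal SDs, b = ρ − 1. With equal arms, the baseline gap has SD s/√(2n), so the 1-SD shift on the fold scale is 10^(|b|·s/√(2n)). For ρ = 0.5: 10^(0.5 × 0.5/√420) = 10^0.0122 = 1.028. On an assumed fold rise of 10^0.4 = 2.51, that is 2.58 instead of 2.51. At 70 per arm and ρ = 0.5 the factor is 1.050.

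**Interval.** Let R² be the squared correlation of the rise with baseline; with equal SDs, R² = (1 − ρ)/2. In units of Var(diff)/n:

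- variance used by the LS-mean CI: 1 − R²
- variance of the unadjusted mean: 1
- variance of the LS mean as an estimate of the population GMFR: (1 − R²) + R²/2 = 1 − R²/2, because the overall baseline mean is itself estimated from 2n subjects

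So printed/unadjusted width = √(1 − R²), printed/correct width = √[(1 − R²)/(1 − R²/2)], and coverage = 2Φ(1.96 × the latter) − 1.

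| ρ | R² | printed/unadjusted | printed/correct | coverage | 1-SD shift, n = 210 |
|---|---|---|---|---|---|
| 0.2 | 0.40 | 0.775 | 0.866 | 91.0% | 4.6% |
| 0.3 | 0.35 | 0.806 | 0.888 | 91.8% | 4.0% |
| 0.5 | 0.25 | 0.866 | 0.926 | 93.0% | 2.8% |
| 0.7 | 0.15 | 0.922 | 0.959 | 94.0% | 1.7% |
| 0.8 | 0.10 | 0.949 | 0.973 | 94.4% | 1.1% |
| 0.9 | 0.05 | 0.975 | 0.987 | 94.7% | 0.6% |

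**Simulation check** (3,000 to 4,000 trials per setting, 210 per arm, average of the two arms). Coverage of the printed interval was 92.4% (ρ = 0.3), 92.9% (0.5) and 94.3% (0.8). With two-fold titers and values below 10 set to 5, as SAP 6.3.5 prescribes for HI, it was 93.5% (ρ = 0.5) and 95.1% (ρ = 0.8).

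**Unequal variances.** The model has one pooled residual variance. With Day 21 SDs of 0.6 and 0.4 (ρ = 0.5), coverage was 88.3% and 96.7%. With 0.65 and 0.45 (ρ = 0.8) it was 91.4% and 97.8%, and the second arm's interval was 1.13 times the unadjusted width.

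The within-arm t interval covered 94.6% to 95.5% in every setting simulated.

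**The case against.** The SAP says in three places that GMFR comes from an ANCOVA, so the estimator is prespecified. Under 1:1 randomisation it targets essentially the same population value as the unadjusted mean, and adjustment brings real precision. The endpoint wording is itself loose, since it speaks of a ratio of GMTs. GMFR has no success threshold; the 30% and 60% lower-bound criteria in Protocol 12.6.1 concern HI seroconversion and seroprotection. On this view a label would be enough.

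Most of that stands, and it limits the point. The loose wording does not rescue the derivation: on paired data the geometric mean of individual ratios and the ratio of GMTs are the same number, and neither is adjusted. Prespecifying the estimator in one section does not reconcile it with the definition kept in others, and section 12 is silent.

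A reader might go further and infer that the printed CI is always too narrow, by the full gap to the unadjusted interval (13% at ρ = 0.5, from 1 − 0.866). The documents do not support that. Part of the gap is legitimate precision gain; against the correct standard error the shortfall at ρ = 0.5 is 7%. With zero slope there is no shortfall, and with unequal variances one arm's interval can be too wide. Nor do the documents give the correlation or the SDs that any such size needs.

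**Conclusion.** The point holds as a minor correction. The SAP defines one statistic and prints another under the same name, without declaring the change; this follows from the text alone. The size is modest: a 1-SD shift of 0.6% to 4.6% at 210 per arm, and coverage of about 91% to 94.7% with similar arm variances, both conditional on the assumed correlations (0.2 to 0.9) and, for the shift, on an SD of 0.5. Unequal variances can miscalibrate the two arms in opposite directions.

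It would be wrong to conclude that the ANCOVA estimates a different population quantity or that the between-arm comparison is at fault. ANCOVA is appropriate there. GMFR is secondary and descriptive, and no non-inferiority or superiority conclusion on efficacy depends on it.

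**What to change.** In SAP 6.3.5, 9.2 and 9.2.2.1, report each arm's GMFR as 10^mean(log10 Day 21 − log10 Day 0) with a within-arm t-based 95% CI. Keep the ANCOVA for the comparison: add the LS-mean difference to the code (for example with the `DIFF` option), back-transform it and its limits, and label it as the baseline-adjusted GMFR ratio. If adjusted per-arm values are also wanted, label them as adjusted and list them in section 12.

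The cost is a few lines of SAS and somewhat wider per-arm intervals: by a factor of 1/0.949 = 1.05 at ρ = 0.8, 1/0.866 = 1.15 at ρ = 0.5 and 1/0.806 = 1.24 at ρ = 0.3, under the same assumptions. The between-arm comparison loses no precision.
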